### 15.2.3.2 European Organization for Research and Treatment of Cancer (EORTC) QLQ-C30

The QLQ-C30 self-assessment questionnaire incorporates five functional scales (Physical, Role, Cognitive, Emotional, and Social), a global health status / HRQoL scale, and a number of single items assessing additional symptoms commonly reported by cancer subjects (e.g. dyspnea, loss of appetite, insomnia, constipation, and diarrhea), and financial impact of the disease (Table 6).

All of the scales and single-item measures range in score from 0 to 100. A high scale score represents a higher response level. Therefore, a high score for a functional scale represents a high/healthy level of functioning and a high score for the global health status / HRQoL scale represents a high overall quality of life, but a high score for a symptom scale/item represents a high level of symptomatology/problems. The scoring procedure for each of the scales is the same and consists of computing the raw score (RS) and then computing the actual scale score (S) by making a linear transformation to standardize the score to values from 0 to 100 as shown below.

$$\text{Raw Score} = \text{RS} = (I_1 + I_2 + \dots + I_n) / n$$

For **Functional scales**:

$$\text{Score} = 100 \times [1 - (\text{RS} - 1) / \text{Range}]$$

For **Symptom scales / items** and **Global health status / HRQoL scale**:

$$\text{Score} = 100 \times [(\text{RS} - 1) / \text{Range}]$$

---

Where  $I_1, I_2, \dots, I_n$  are the individual items and Range is the difference between the maximum possible value of RS and the minimum possible value. The range of RS equals the range of the item values. Most items are scored 1 to 4, giving Range = 3. The exceptions are the items contributing to the Global Health Status / HRQoL scale, which are 7-point questions with Range = 6.

**Table 6** **QLQ-C30 Global Health Status and Functional Scales**

Scale	Items
Global Health Status / HRQoL scale	
Global Health Status / HRQoL scale	29, 30
Functional Scales	
Physical Functioning	1, 2, 3, 4, 5
Role Functioning	6,7
Emotional Functioning	21, 22, 23, 24
Cognitive Functioning	20, 25
Social Functioning	26, 27
Symptom Scales / Items	
Fatigue	10, 12, 18
Nausea and vomiting	14, 15
Pain	9, 19
Dyspnoea	8
Insomnia	11
Appetite loss	13
Constipation	16
Diarrhoea	17
Financial difficulties	28

If 50% or more of the items for a given scale are non-missing, then the Raw Score should be computed as the average of the non-missing items; if more than 50% of the items for a given scale are missing the scale score will be set to missing.

### 15.2.3.3 European Organization for Research and Treatment of Cancer (EORTC) Gastric Cancer Module QLQ-STO22

The QLQ-STO22 self-assessment questionnaire is a gastric cancer module consisting of 22 items concerning disease and treatment-related symptoms and side effects, dysphagia, nutritional aspects and items about the emotional problems of gastric cancer. The module is composed of 5 multi-item symptom scales (Dysphagia, Pain, Reflux, Eating Restrictions, and Anxiety) and four single items (Dry Mouth, Tasting, Body Image, and Hair Loss) as shown in Table 7. A higher score represents more problems/ worse symptom severity.

**Table 7**                      **QLQ-STO22 Multi-Item Symptom Scales**

Scale	Items
Dysphagia	31, 32, 33
Pain	34, 35, 36, 37
Reflux	38, 39, 40
Eating Restrictions	41, 42, 43, 46
Anxiety	47, 48, 50
Dry Mouth	44
Taste	45
Body Image	49
Hair Loss	51, 52

The same scoring methodology will be used for the QLQ-STO22 as for the QLQ-C30.

CCI

CCI

CCI

[Redacted]

CCI

CCI

CCI

---

[Redacted]

The primary endpoint of OS time between the two treatment arms will be analyzed using a two-sided unstratified log rank test by PD-L1 expression status; the unstratified HR and its corresponding 95% CI will be computed by PD-L1 expression status as well. Details of the analysis are specified in Section 16.1.4.

The confirmed ORR by treatment group will be calculated along with the two-sided 95% CI using the Clopper-Pearson method by PD-L1 expression status. The association of treatment effect and ORR will be tested by PD-L1 expression status with the same CMH method as described in Section 15.2.2.

## 16 Safety Evaluation

The subsections in this section include specifications for summarizing safety endpoints that are common across clinical trials such as adverse events, laboratory tests and vital signs. All safety related summary tables will be summarized for the on-treatment period of the Induction and/or Maintenance Phase and the analysis sets specified in Table 8. The safety endpoints will be tabulated using descriptive statistics.

**Table 8 Safety Analyses by Analysis Set and Study Phase**

	Safety – Induction Analysis Set	Safety-Maintenance Analysis Set	
	Induction Phase	Induction Phase	Maintenance Phase
AEs			
Overall Summary by Category	Y	Y	Y
All TEAEs	Y	Y	Y
Related TEAEs	Y	Y	Y
Serious TEAEs	Y	Y	Y
NCI CTC AE Toxicity Grades	Y	Y	Y
AEs Leading to Discontinuation	Y		Y
AEs Leading to Death	Y		Y
irAEs			Y
IRRs			Y
Labs			
Descriptive Statistics		Y	Y
NCI CTCAE Toxicity	Y	Y	Y
Shifts Relative to Normal Range			Y
Vital Signs			
Descriptive Statistics			Y
Change Categories			Y
ECG			
Descriptive Statistics			Y
PCSA Criteria	Y	Y	Y

## 16.1 Adverse Events

Treatment-emergent adverse events (TEAEs) are those events with onset dates occurring during the on-treatment period or if the worsening of an event is during the on-treatment period. In this study, there are two on-treatment periods, one for Induction Phase and one for Maintenance Phase.

All analyses described will be based on TEAEs (started during the on-treatment period) if not otherwise specified. The AE listings will include all AEs (whether treatment-emergent or not). AEs outside the on-treatment period will be flagged in the listings.

- **Related Adverse Events:** adverse events with relationship to study treatment (as recorded on the AE eCRF page, Relationship with study treatment = Related) reported by the investigator and those of unknown relationship (i.e. no answer to the question “Relationship with study treatment”).
- **Serious Adverse Events (SAE):** serious adverse events (as recorded on the AE eCRF page, Serious Adverse Event = Yes).
- **Adverse Events Leading to Treatment Discontinuation:** adverse events leading to permanent discontinuation of study treatment (as recorded on the AE eCRF page, Action taken with study treatment = Drug withdrawn).
- **Adverse Events Leading to Death:** adverse event leading to death (as recorded on the AE eCRF page, Outcome = Fatal, as well as AEs of Grade 5).
- **Immune Related Adverse Events (irAEs):** immune related adverse events are identified via customized MedDRA PT queries and additionally classified by medical assessment according to case definition (two level approach). Details are included in [Appendix IV](#).
- **Infusion Related Reactions (IRRs):** IRRs are identified based on a list of MedDRA PTs. The detailed criteria of the timing relationship to infusion are specified in [Table 14](#) of Appendix IV.

Unless otherwise specified, AEs will be summarized by number and percentage of subjects with the AE in the category of interest as described above, by treatment group, primary System Organ Class (SOC) and Preferred Term (PT) and by decreasing frequency based on the avelumab treatment arm.

Each subject will be counted only once within each SOC or PT. If a subject experiences more than one AE within a SOC or PT for the same summary period, only the AE with the strongest relationship or the worst severity, as appropriate, will be included in the summaries of relationship and severity.

Within one adverse event, changes in toxicity grade, seriousness, or outcome are recorded as separate AE entries in the eCRF with start and end dates corresponding to the dates of change. In such cases, the start date of one entry will equal the end date of a previous entry. In the case that records report an event with the same preferred term in immediately consecutive periods and the severity of the reported event does not worsen, the records will be considered as one event in the analysis. All events will be maintained as separate records in the database, in order to maintain the full detailed history of the events and preserve traceability. The start date of the initial record in the sequence is

---

taken as start date of the entire event. Duration of the AE and the TEAE flag will be adjusted accordingly in the analysis. In the case that a subsequent record indicates a worsening of an ongoing event, the subsequent, worse record will be treated as a separate adverse event. If the subsequent, worse record is outside of the on-treatment period, it will not appear on the summaries/listings of TEAEs.

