5.1.3.3 Dose Modification for Chemotherapy

During the Induction Phase, dose modifications (dose delays and dose changes) for toxicity after the starting dose are allowed and should be made in accordance with labeling instructions and local institutional guidelines. Subjects on chemotherapy in the Maintenance Phase will continue with the same dose they had at the end of the Induction Phase (starting dose or reduced dose). During the Maintenance Phase, dose modifications are also allowed for toxicity.

The dose of chemotherapy will be calculated based on the weight or body surface area, as applicable, of the subject determined within 72 hours prior to the day of drug administration (see Table 9).

Dose modification guidelines (dose delays and dose changes) after the starting dose for chemotherapy are provided in Table 8. For specific starting doses due to renal or hepatic impairment and for subsequent dose modifications due to different toxicities, please follow the local label and guidelines.

For subjects intolerant to further oxaliplatin, single-agent capecitabine or 5-FU + leucovorin will be an option for dose modification.

Table 8 Dose Modification General Guidelines for Chemotherapy

Maintenance Therapy	First Dose Reduction	Second Dose Reduction	Third Dose Reduction
5-FU (2600 mg/m ² dose over 24 hours)	1950 mg/m ² - 2080 mg/m ² over 24 hours	1300 mg/m ² (1560 mg/m ² over 24 hours)	Discontinue
5-FU (2400 mg/m ² dose) over 46-48 hours	1800 mg/m ² - 1920 mg/m ² over 46-48 hours	1200 mg/m ² -1440 mg/m ² over 46-48 hours	Discontinue
Capecitabine	75% of starting dose	50% of starting dose	Discontinue
Oxaliplatin (85 mg/m ² dose)	64 to 68 mg/m ² in accordance with local label/institutional guidelines	42.5 mg/m ² in accordance with local label/institutional guidelines	Discontinue
Oxaliplatin (130 mg/m ² dose)	98 to 104 mg/m ² in accordance with local label/institutional guidelines	65 mg/m ² in accordance with local label/institutional guidelines	Discontinue

5-FU=5-fluorouracil

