8.5.5 Analysis of Safety Endpoints

All Safety analyses will be performed on the Safety-Maintenance Analysis Set unless otherwise noted. Safety endpoints will be tabulated using descriptive statistics only.

Safety assessments will be based on review of AEs, concomitant medications, local laboratory measurements (serum chemistry, hematology, and urinalysis), ECOG PS, physical examinations, body weight, vital signs, and 12-lead ECGs.

Adverse Events

All AEs will be coded according to the Medical Dictionary for Regulatory Activities (MedDRA) dictionary (Version 20.1). Severity of AEs will be graded using the NCI-CTCAE v 4.03 toxicity grading scale.

Treatment-emergent AEs (TEAEs) are defined as events with onset dates occurring on-treatment or events which worsen on-treatment (see Section 7.4.1.2). TEAEs are defined separately for the Induction and Maintenance Phases. Unless otherwise specified, summaries will be performed on Maintenance Phase TEAEs.

The incidence of TEAEs, regardless of relatedness to treatment, will be summarized by System Organ Class and Preferred Term for each treatment arm. Similar summaries will also be provided for treatment-emergent serious adverse events (TESAEs), TEAEs leading to permanent discontinuation of treatment, TEAEs by maximum severity, TEAEs by highest relationship to treatment, TEAEs with fatal outcome, and TEAEs of special interest (AESIs) such as irAEs.

The incidence of TEAEs and TESAEs during the Induction Phase will be summarized by system organ class/preferred term by total number of subjects.

Concomitant Medications and Procedures

Concomitant medications (ie, medications other than trial treatment taken at any time on-treatment) will be summarized for the Maintenance Phase using frequencies and percentages within a given drug class and preferred name by treatment arm and overall. Concomitant procedures (ie, procedures undertaken at any time on-treatment) will be listed only.

Laboratory Values

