### 16.1.2 Adverse Events Leading to Treatment Discontinuation

*Analysis sets: Safety-Induction Analysis Set, Safety-Maintenance Analysis Set*

The frequency (number and percentage) of subjects with each of the following will be presented for TEAEs leading to permanent discontinuation by treatment group:

- TEAEs leading to treatment discontinuation by SOC and PT
- Related TEAEs leading to treatment discontinuation by SOC and PT

A listing of all TEAEs leading to treatment discontinuation will also be provided, including the relevant information.

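### The by-arm Maintenance tables of AEs leading to treatment discontinuation omit withdrawals caused by an AE that began in Induction and did not worsen, an omission likely to fall mainly on the control arm

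*SAP*

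**What the plan says.** SAP 16.1 defines TEAEs as "those events with onset dates occurring during the on-treatment period or if the worsening of an event is during the on-treatment period". It adds: "In this study, there are two on-treatment periods, one for Induction Phase and one for Maintenance Phase". Protocol 8.5.5 agrees: "TEAEs are defined separately for the Induction and Maintenance Phases". Under SAP 10, the Maintenance period for subjects on active treatment opens at the first dose of randomized treatment.

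The default basis for the AE summaries is: "All analyses described will be based on TEAEs (started during the on-treatment period) if not otherwise specified". An AE leading to discontinuation is recognised from the AE page of the eCRF, when the action taken with study treatment is drug withdrawn. The overall summary in 16.1.1 and the SOC/PT tables in 16.1.2 then count only TEAEs with that action.

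On listings, 16.1 states: "The AE listings will include all AEs (whether treatment-emergent or not", with those outside the on-treatment period flagged. Section 16.1.2 describes its own listing more narrowly: "A listing of all TEAEs leading to treatment discontinuation will also be provided, including the relevant information".

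On treatment, Protocol 5.1.2.2.2 and 5.1.3.3 have control subjects continue their Induction regimen at the dose reached at the end of Induction, reduced or not. They also provide: "For subjects intolerant to further oxaliplatin, single-agent capecitabine or 5-FU + leucovorin will be an option for dose modification".

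**The concern.** The two arms enter Maintenance with different exposure histories. Avelumab is first given after randomization, so a reaction to it will normally have its onset in Maintenance. Control subjects on chemotherapy have already had 12 weeks of the same drugs. A toxicity can begin in Induction, stay at one grade and eventually lead to a drug being stopped in Maintenance. The stopping is an event on randomized treatment, but the table filter looks at when the AE began or worsened, not at when the drug was withdrawn.

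Safety and tolerability is a stated secondary objective (Protocol 4.2), and AE-related discontinuation by arm is one of the figures readers will use to judge it. If such cases occur, the AE table will show fewer withdrawals than the disposition table, and neither 11.1 nor 16.1.2 says how to reconcile the two.

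**Working it through.** The documents give no figure to reproduce, so the check is a reading of the rules in sequence. Take a control subject whose toxicity starts in Induction, does not worsen, and leads to withdrawal of a Maintenance drug.

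1. **Onset.** The AE starts before the first randomized dose, so it fails the onset test for a Maintenance TEAE (SAP 10 and 16.1).
2. **Worsening.** There is none, so it fails the second test.
3. **Record handling.** SAP 16.1 says that changes in grade, seriousness or outcome create separate entries. A change in action taken is not on that list. If another change does split the record, immediately consecutive entries with the same preferred term and no worsening are treated as one event, dated to the first entry, and the TEAE flag is adjusted to match. The event therefore keeps its Induction onset whether there is one record or several.
4. **Table layout.** SAP Table 8, for AEs leading to discontinuation:

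| Analysis set | Induction Phase | Maintenance Phase |
|---|---|---|
| Safety-Induction | Y | not a column |
| Safety-Maintenance | blank | Y |

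The Safety-Maintenance/Maintenance table excludes the case by steps 1 to 3, and no Induction table is planned for that set. The Safety-Induction table may pick it up, because the AE is an Induction TEAE with drug withdrawn as its action. That table is presented by Induction regimen and overall (SAP 10), not by randomized arm, and it would attribute to Induction a withdrawal that happened on randomized treatment.
5. **Elsewhere in the report.** The Maintenance disposition table (SAP 11.1) counts, by randomized arm, subjects who discontinued any one study drug, with primary reason by drug. It has no TEAE filter, so the withdrawal appears there.

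**Scale, on assumed rates only.** With 499 subjects randomized 1:1, each arm has about 499 / 2 = 249.5 subjects. If the share of control subjects affected were:
- 1%: 0.01 × 249.5 ≈ 2.5 subjects
- 2%: 0.02 × 249.5 ≈ 5 subjects
- 5%: 0.05 × 249.5 ≈ 12.5 subjects

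None of these rates comes from the documents. The base is also too large, because the control arm includes BSC-only subjects, who have no drug to withdraw.

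**The case against.** Several rules limit the point, and most of them stand.

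- **Listings.** A reader might infer that these cases disappear even from the listings. The documents do not support that. Section 16.1 says AE listings cover all AEs. The 16.1.2 listing is not confined to Maintenance, its heading covers both safety sets, and an Induction-onset toxicity is normally a TEAE of the Induction period. What remains is a difference in wording between the two sections.
- **Disposition.** A reader might also infer that the withdrawals go uncounted by arm anywhere. They do not: SAP 11.1 counts them. The gap is confined to the AE-discontinuation tables.
- **Narrow group.** Toxicity that worsens in Maintenance is treated as a separate AE and is counted, and cumulative toxicity often does worsen with continued dosing. Eligibility is reviewed again before randomization, and exclusion criterion 13 bars persisting Grade 2 or higher toxicity from prior therapy. Subjects unfit for further chemotherapy are designated BSC-only beforehand. Completely missing onset dates are imputed to the start of randomized treatment (SAP 10), which moves some doubtful AEs into Maintenance. These rules shrink the group without emptying it. Criterion 13 does not say whether prior therapy includes Induction chemotherapy, neuropathy has its own higher threshold (Grade 3, criterion 14), and Grade 1 toxicity may carry over on any reading.
- **Same rule in both arms.** Avelumab subjects also arrive with chemotherapy toxicity and could stop for it. The conclusion that control is made to look better tolerated is therefore an inference from exposure history, not something the documents show.
- **Prespecified and descriptive.** Protocol 8.5.5 sets the TEAE basis and the SAP follows it. No test or alpha depends on it. This is true, but it does not make the table a complete count of AE-related withdrawals from randomized treatment.

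**Conclusion.** The point holds in a limited form. By rule, the Maintenance AE-discontinuation tables in SAP 16.1.1 and 16.1.2 leave out withdrawals of Maintenance treatment caused by an Induction-onset AE that did not worsen, and those withdrawals may be placed in the Induction discontinuation table. This follows from the text and needs no assumption.

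That the omission falls mainly on control is plausible, because only control continues the Induction drugs, but it is not demonstrated. Its size is unknown: the documents report neither how many subjects carry toxicity into Maintenance nor how many later stop for it at an unchanged grade. No efficacy conclusion or error rate is affected. What changes is a reported tolerability figure and its agreement with the disposition table.

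**What to change.** In SAP 16.1.1 and 16.1.2, add a count by randomized arm in the Safety-Maintenance set. It should include every AE with drug withdrawn as the action where study treatment was withdrawn during Maintenance, whatever the phase of onset. Identify the timing from Maintenance dosing and drug-discontinuation dates rather than from AE onset.

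Alongside this:
- keep the TEAE-only count as a sub-row;
- state that these withdrawals are not counted as Induction discontinuations;
- reconcile the new count with the disposition reasons by drug in SAP 11.1, and explain any remaining difference;
- reword the 16.1.2 listing so that it agrees with the all-AE rule in 16.1.

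The cost is SAP wording, one further filter and one more table row. The control discontinuation rate may look less favourable as a result.

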5.1.1 Overall Design

Approximately 466 subjects are planned to be enrolled in the Maintenance Phase. The actual number of subjects enrolled in the Induction Phase will be driven by observed induction failure rates and will be such to allow for approximately 466 patients to be randomized in the Maintenance Phase. At the time of this protocol amendment, subject enrollment in the Maintenance Phase is complete, with 499 subjects randomized into the Maintenance Phase. Subjects enrolled in the Induction Phase will receive a first-line therapy comprised of oxaliplatin and either 5-FU or capecitabine (Induction Phase) for 12 weeks (see Section 5.1.2.1).

Following the Induction Phase, subjects who experience a CR, PR, or SD after 12 weeks (approximately 466 subjects) will be randomly assigned (Maintenance Phase) to receive either avelumab (see Section 5.1.2.2.1) or continuation of the same regimen of chemotherapy from the Induction Phase (see Section 5.1.2.2.2). Subjects who are not deemed eligible to receive further chemotherapy will receive best supportive care (BSC) alone with no active therapy.

Prior to randomization, Investigators must specify which of treatments (continuation of the same regimen of chemotherapy from the Induction Phase versus BSC) will be selected for subjects in chemotherapy control arm.

CCI

After the Induction Phase, all subjects will be evaluated for eligibility into the Maintenance Phase by an independent radiologist using RECIST v1.1.

Study treatment will continue until:

- Disease progression (see Section 5.5.1)
- Significant clinical deterioration (clinical progression) by Investigator's opinion
- Unacceptable toxicity per Investigator opinion, or
- Any criterion for withdrawal from the trial or trial treatment is fulfilled (see Section 5.5).

Subjects receiving avelumab may continue treatment past the initial determination of disease progression per RECIST v1.1 as long the following criteria are met:

- Investigator-assessed clinical benefit, without any rapid disease progression
- Tolerance of trial treatment
- Stable Eastern Cooperative Oncology Group (ECOG) performance status (PS) (PS = 0 or 1)
- Treatment beyond progression will not delay an imminent intervention to prevent serious complications of disease progression (for example, central nervous system metastases).

The decision to continue avelumab treatment beyond progression should be discussed with the Medical Monitor and documented in the study records.

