5.2.3 Rationale for Switching Subjects from Chemotherapy to Avelumab

The proposal to switch subjects assigned to the experimental arm after they have completed 12 weeks of chemotherapy is appropriate for the following reasons:

- There is no data supporting that additional chemotherapy beyond 4 to 6 cycles (up to 12 weeks of treatment) will result in improved survival in the context of a disease where it is common practice to re-induce patients at the time of disease progression. Patients who have not responded to or who will cease to respond to avelumab will be re-induced either with platinum-based doublets or with drugs that have shown clinical benefit as a second-line therapy. Subjects will be monitored every 6 weeks and rescue therapy may be administered once disease progression is established.
- Treatment of patients with avelumab has resulted in an ORR of 15% in patients with gastric cancer from Asian and non-Asian regions. Some of these responses were long lasting and a number of subjects with prolonged SD were also observed. Based on these data, it is reasonable to interrupt chemotherapy after 12 weeks to initiate an immunotherapy that has been reported to induce prolonged responses in advanced gastric cancer patients who will ultimately progress after initial chemotherapy regimens.
- For subjects randomly assigned to receive additional chemotherapy in the Maintenance Phase, it is recommended that the chemotherapy regimen does not to exceed 6 cycles. This is supported by the previously established regimen in the registration study for trastuzumab (TOGA). In conclusion, switching subjects after 12 weeks of chemotherapy to receive avelumab treatment is considered appropriate.

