**Definition of On-Treatment period:**

For the Induction Phase, the on-Treatment period is defined as the time from the first dose of induction chemotherapy treatment through the earliest of (the date of the last dose of Induction chemotherapy + 30 days, start day of new anti-cancer drug therapy – 1 day, date of Maintenance Phase study treatment start – 1 day).

For subjects randomized to the avelumab arm or the control arm and receive chemotherapy, the on-treatment period is defined as the time from the first dose of randomized treatment through the earliest of (last dose of study treatment + 30 days, start day of subsequent anti-cancer drug therapy – 1 day). For subjects randomized to the control arm and receive BSC-only, study treatment is considered to start on the day of the Week 1 Day 1 assessment visit and end on the earliest date given from among the following: date given on the Study Termination eCRF page and date of death. Thus, the on-treatment period for these subjects is defined as the time from the Week 1 Day 1 assessment visit to the earlier of (end of assessment date + 30 days, start of new anti-cancer drug therapy – 1 day).

The date of subsequent anti-cancer drug therapy is derived as outlined in Section 13.2.

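### If on-treatment times differ between arms, the crude adverse-event percentages mix toxicity rate with time at risk, and the visible SAP text plans no exposure-adjusted summary

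*SAP*

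**What the plan says.** **How events are counted.** SAP 16.1 states that "AEs will be summarized by number and percentage of subjects with the AE in the category of interest", by treatment group, and that "Each subject will be counted only once within each SOC or PT". Sections 16.1.1, 16.1.2, 16.2.2 and 16.2.3 apply this to treatment-emergent events (TEAEs) overall, Grade 3 or higher, related, serious, leading to discontinuation, fatal, potential immune-related (irAE) and infusion-related. Protocol 8.5.5 adds that "Safety endpoints will be tabulated using descriptive statistics only".

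**The window.** For subjects on active treatment, SAP Section 10 defines it as the "time from the first dose of randomized treatment through the earliest of (last dose of study treatment + 30 days" or the day before a subsequent anti-cancer drug therapy). BSC-only subjects have their own window, from the Week 1 Day 1 visit, and are counted in the control arm. SAP 14 leaves BSC out of the exposure calculation.

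**How long treatment lasts.** Protocol 5.1.2.2.2, 6.2.2 and 7.1.4 let control chemotherapy end at the maximal duration accepted for the agent, and 6.2.2 stops it at first radiological progression. Protocol 5.2.3 says that "it is recommended that the chemotherapy regimen does not to exceed 6 cycles". For avelumab, 5.2.6 gives progression or unacceptable toxicity as the end and names no maximum. Section 5.1.1 adds that "Subjects receiving avelumab may continue treatment past the initial determination of disease progression per RECIST v1.1", subject to criteria.

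**The concern.** A crude percentage over a treatment-dependent window rises with the length of that window even when the underlying hazard does not change. The stopping rules differ by arm, so the windows may differ too. Safety and tolerability of avelumab is a secondary objective (Protocol 4.2), and most of these tables set the two arms side by side. A reader who takes the difference between two columns as a difference in toxicity may be seeing a difference in time at risk. The SAP 16.1.1 table of events reaching 5% in any arm is affected in the same way, because a longer window brings more terms over the threshold. Treatment duration is summarised in SAP 14, but no visible adverse-event table uses it.

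**Working it through.** The documents give no adverse-event rate, expected exposure or safety power, so there is no figure of theirs to reproduce. The hazards, progression times and avelumab windows below are assumptions.

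**1. Fixed windows.** Crude incidence = 1 − exp(−h × t), with a constant hazard h equal in both arms and t the on-treatment window.

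Control windows under a hypothetical cap of 6 maintenance cycles:
- 5-FU: sixth dose on Day 71 (Table 4), so (70 + 30)/30.4375 = 3.29 months.
- Capecitabine: (5×21 + 13 + 30)/30.4375 = 4.86 months.

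| h per month | Control 3.29 | Control 4.86 | Avelumab 3 | Avelumab 7 | Avelumab 13 |
|---|---|---|---|---|---|
| 0.03 | 9.4% | 13.6% | 8.6% | 18.9% | 32.3% |
| 0.06 | 17.9% | 25.3% | 16.5% | 34.3% | 54.2% |

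The extreme apparent ratios are 8.6/13.6 = 0.63 and 32.3/9.4 = 3.4. The true ratio is 1 throughout.

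**2. Letting control subjects progress before the cap.** Let time to progression be exponential with rate g = ln 2/median, equal in both arms, plus 30 days (0.986 months).
- No cap: incidence = 1 − exp(−0.986h) × g/(g+h).
- Cap c: replace g/(g+h) by g/(g+h) × (1 − exp(−(g+h)c)) + exp(−(g+h)c).

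With median 6 months and h = 0.10, g = 0.1155, g/(g+h) = 0.536 and exp(−0.0986) = 0.906.
- Avelumab, no cap: 1 − 0.906 × 0.536 = 51.4%.
- Control, c = 70/30.4375 = 2.30 months: 1 − 0.906 × 0.819 = 25.8%.
- Control, c = 118/30.4375 = 3.88 months: 1 − 0.906 × 0.737 = 33.2%.

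The gap with no difference in hazard is 25.6 or 18.2 points. Over medians of 3 to 9 months, hazards of 0.05 to 0.20 and zero or 6 weeks of avelumab past progression, it runs from about 6 to 39 points.

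**3. Where the effect vanishes or reverses.** With no cap, no dosing past progression and equal progression times, both arms show 51.4%. If median time to progression is 2 months on avelumab and 6 months on control with the 3-week-cycle cap, avelumab shows 29.7% and control 33.2%.

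**4. Check of the remedy.** Expected time to first event or window end is (1 − exp(−ht))/h per subject, so subjects with an event divided by that time returns h. For h = 0.06: 0.179/2.98 = 0.06 at 3.29 months and 0.542/9.03 = 0.06 at 13 months.

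**The case against.** The case against has real substance, and it limits the point in five ways.

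- **The 6-cycle cap.** A reader might treat it as the operative rule. It is a recommendation within a design rationale. Tables 3 and 4 schedule chemotherapy at every visit and then every 3 or 2 weeks until progression, and Table 4 already shows a seventh dosing visit. Protocol 5.2.6 leaves the maximum to the investigator. The ratio of 3.4 also pairs the longest assumed avelumab window with the shortest control window.
- **The extent.** A reader might conclude that every between-arm table is affected and that nothing on timing is planned. The SAP contents show a redacted entry after 16.2.3, so only the visible text can be judged. Medically assessed irAE tables show avelumab alone. Section 16.2.3 does plan first onset of infusion-related reactions by infusion number, and 16.2.1 has a fixed 60-day death table.
- **Interpretability.** It is tempting to call the comparison uninterpretable. The documents do not support that. The safety analysis is descriptive, the safety objective is not worded as a comparison, and the share of subjects with an event under the regimen as delivered is a legitimate quantity. Duration and dose intensity are also tabulated.
- **Constant hazard.** Early-onset events depend less on duration, and for these a person-time rate can flatter the longer-treated arm.
- **BSC-only subjects.** Pooling their person-time into the control rate would dilute chemotherapy toxicity.

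What remains is that the window follows treatment duration, the stopping rules differ by arm, and the visible text offers no summary that separates rate from time at risk.

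**Conclusion.** The point holds conditionally. If realised on-treatment times differ, equal hazards will appear as different crude percentages. The design permits such a difference, but its size and direction depend on realised durations and cannot be read from the documents. An apparent ratio of about 0.6 to 3.4 for a true ratio of 1 rests on a constant equal hazard of 0.03 to 0.06 per month, a hypothetical 6-cycle control cap and avelumab windows of 3 to 13 months. It illustrates the mechanism and does not forecast the result. With equal durations the distortion is nil. No adverse-event hypothesis is tested, so type I error is untouched. What is affected is how far the safety tables support a statement about relative toxicity.

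**What to change.** Keep the crude tables. In SAP 16.1.1 and 16.2.2, add an exposure-adjusted first-event rate per arm for the overall-summary categories shown in both arms: TEAE, Grade 3 or higher, related, serious, leading to discontinuation, and potential irAE. The rate is the number of subjects with a first event divided by total on-treatment time to first event or window end.

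Take person-time from the SAP Section 10 on-treatment period, including its cut-off at subsequent anti-cancer drug therapy. The SAP 14 exposure calculation cannot serve, because it leaves out BSC-only subjects who are in the control denominator. Show the control rate overall and separately for chemotherapy-treated and BSC-only subjects.

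Add a cumulative incidence curve by arm for first Grade 3 or higher TEAE, with death and the end of the on-treatment period for other reasons as competing events. Subjects still on treatment at data cut-off should be censored.

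The cost is SAP wording, one table and one figure, built from dosing and onset dates already collected. The rate assumes a roughly constant hazard and suits early-onset events poorly, which is why the curve should accompany it.

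Separately, the statements on control duration in the Synopsis, Protocol 5.1.2.2.2, 5.2.3, 5.2.6 and Tables 3 and 4 must be reconciled, including whether induction cycles count toward the 6. No view is taken here on which is right.
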